11.4. Population for Analysis Sets

FAS will include all subjects who received at least one dose of study drug. Efficacy analyses will be performed using FAS.

Safety Analysis Set will include all subjects who received at least one dose of study drug.

PK Analysis Set will include all subjects in the Safety Analysis Set who have at least one PK sample with measurable concentration for U3-1402 (ADC, total anti-HER3 Ab, or MAAA-1181).

11.5. Statistical Analyses

11.5.1. Efficacy Analyses

11.5.1.1. Primary Efficacy Analyses

The primary efficacy endpoint is ORR (the proportion of subjects with a best overall response [BOR] of CR or PR) as assessed by BICR per RECIST v1.1. CR/PR will be confirmed with a follow-up tumor assessment at least 4 weeks apart.

ORR will be summarized with the 2-sided 95% CI using the Clopper-Pearson method in the FAS. For the computation of ORR, subjects with BOR of “not evaluable (NE)” will be included in the FAS and will be considered non-responders. Data will be summarized by cohort if applicable. No formal comparison between the 2 cohorts is planned.

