11.3. Sample Size Determination

In Part 1 of the study, approximately 36 subjects will be evaluated in the two cohorts. If both Cohort 1 and Cohort 2 advance to Part 2 of the study, approximately 44 additional subjects will be enrolled in Part 2 (regardless of HER3 IHC status). In such a circumstance, approximately 80 subjects will be enrolled in total. If only Cohort 1 advances to Part 2 of the study, approximately 44 additional subjects will be enrolled in Part 2. In such circumstance, approximately 80 subjects will be enrolled in total (68 of 80 subjects will have HER3 high expressing tumors).

The total sample size is shown in [Table 11.1](#).

Table 11.1: Total Sample Size Pre- and Post-futility Analysis

| | Scenario 1 Enrollment continues in both Cohorts | | Scenario 2 Enrollment continues in Cohort 1 only | |
|---------------------------------------|--|-----------------|---|----------|
| | Cohort 1 | Cohort 2 | Cohort 1 | Cohort 2 |
| Futility decision per cohort | Go | Go | Go | Stop |
| Sample size up to futility | 24 | 12 | 24 | 12 |
| Additional sample size after futility | | 44 ^a | 44 | NA |
| Cohort sample size | | 80 ^a | 68 | 12 |
| Total sample size for the study | | 80 ^a | | 80 |

HER3 = human epidermal growth factor receptor 3; IHC = immunohistochemistry; NA = not applicable

^a All comers will be enrolled regardless of HER3 IHC status

If the criteria to continue enrollment are not met at interim futility analysis in either cohort, further enrollment will be stopped. In this scenario, the total sample size for the study will be approximately 36 subjects (Cohort 1: 24 subjects, Cohort 2: 12 subjects).

Table 11.2 presents the minimum number of responders at various sample sizes for the 95% exact CIs lower bound to be above 5%.

The clinically meaningful ORR is considered as 20% and the ORR based on historical data is considered as 5%.^{9,10}

With a sample size of 68 subjects, if 8 responses are observed, the observed ORR will be 11.8% with a 95% exact confidence interval (CI) of (5.2%, 21.9%). The probability of observing 8 or more responders in 68 subjects is approximately 97.4% when the true ORR is 20%. If the true ORR is 5%, the probability of observing 8 or more responders in 68 subjects is approximately 2%.

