11.6. Interim Analyses

For each study cohort, review of the preliminary data from Part 1 will be used to determine whether to open Part 2. The decision to advance from Part 1 to Part 2 will be made separately in Cohort 1 and Cohort 2; the interim futility analysis will be conducted with approximately 24 subjects in Cohort 1 and approximately 12 subjects in Cohort 2 after all subjects have had the opportunity to complete two tumor assessments. The tumor assessment period may be extended if emerging data show responses are occurring later, or if the tumor assessment for the final evaluated subject in each cohort is delayed. At the time of the interim analysis for each cohort, enrollment into the respective cohort will be paused until the determination that criteria for advancement to Part 2 has been achieved. Note it is possible for the futility criterion to be passed before the above specified analysis timing. These analyses will be conducted based on BICR assessment in the FAS.

Cohort 1 Decision Criteria at Interim:

1. If at least 3 responders out of 24 subjects in Cohort 1 are observed, then further enrollment in this cohort may proceed.
2. If 0 or 1 responder out of 24 subjects in Cohort 1 is observed at the interim, then further enrollment in this cohort may stop.
3. If 2 responders out of 24 subjects in Cohort 1 are observed, then a decision will be made, after further review of the data, to either continue or stop further enrollment in this cohort.

Cohort 2 Decision Criteria at Interim:

1. If at least 2 responders out of 12 subjects in Cohort 2 are observed, further enrollment in this cohort may proceed after submission of a protocol amendment which includes the preliminary data from Cohort 2 Part 1.
2. If 0 responder out of 12 subjects in Cohort 2 is observed at the interim, then further enrollment in this cohort may stop.
3. If 1 responder out of 12 subjects in Cohort 2 is observed, then a decision will be made, after further review of the data, to either continue or stop further enrollment in this cohort. Further enrollment will be contingent upon submission of a protocol amendment which includes the preliminary data from Cohort 2 Part 1.

The exact decision rules will depend on the actual number of subjects at the respective interim analysis.

If the criterion to pass futility is met at interim for Cohort 2 but not Cohort 1, all data will be reviewed thoroughly to decide the next step for the study.

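### Once Part 2 opens, the pooled ORR overstates a weak drug and its interval ignores the gate; add a pre-specified Part 2-only ORR as a companion

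*Combined protocol and SAP*

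**What the plan says.** Section 11.6 gates Part 2 separately in each cohort on BICR-assessed response, which is also the basis of the primary endpoint: "the interim futility analysis will be conducted with approximately 24 subjects in Cohort 1 and approximately 12 subjects in Cohort 2". For Cohort 1 the rule has three zones.

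- Go: "If at least 3 responders out of 24 subjects in Cohort 1 are observed, then further enrollment in this cohort may proceed".
- Review: "If 2 responders out of 24 subjects in Cohort 1 are observed, then a decision will be made, after further review of the data".
- Stop, worded as permissive: "If 0 or 1 responder out of 24 subjects in Cohort 1 is observed at the interim", enrollment may end.

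Section 11.6 adds that the exact rule depends on the number of subjects at the interim, and that PK and subject or disease characteristics may also weigh in the decision.

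The Part 1 subjects stay in the final analysis. Section 11.4 defines the set without regard to part: "FAS will include all subjects who received at least one dose of study drug". Section 11.5.1.1 gives the estimator and interval, "ORR will be summarized with the 2-sided 95% CI using the Clopper-Pearson method in the FAS", and the level of reporting: "Data will be summarized by cohort if applicable". That is by cohort, not by part.

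Section 11.3 plans around a historical ORR of 5% and a clinically meaningful ORR of 20%. Table 11.2 treats 68 (Scenario 2) or 80 (Scenario 1) as one fixed binomial sample and looks for the smallest count whose exact lower limit clears 5%. Section 11.2 plans no hypothesis test. Sections 11.1 and 11.7 leave detailed methods to a separate SAP, which is not part of the text reviewed. The supplied text mentions no Part 2-only ORR, adjusted estimate or two-stage interval.

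**The concern.** A Cohort 1 result on about 68 subjects will normally exist only if Part 1 passed its gate. Given that, the 24 Part 1 subjects are a selected group whose observed rate tends to lie above the true rate, while the 44 Part 2 subjects are not selected. Pooling them carries part of the selection into the primary estimate, and a fixed-sample interval takes no account of it.

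The effect is largest near 5%, the value the plan uses as its historical benchmark. A reader who sees 8/68 with a lower limit just above 5% cannot tell from the planned outputs how much of it comes from the 24 subjects who opened the gate. With no test planned, the estimate and interval are the primary result.

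**Working it through.** **The plan's own figures reproduce.** For 8/68 the Clopper-Pearson interval is 5.2% to 21.9%, with P(X≥8) = 97.4% at 20% and 2.0% at 5%. At 7/68 the lower limit is 4.2%, so 8 is the smallest count that clears 5%. The interim probabilities also agree: P(≥3/24) = 88.5% at 20%, and P(0 or 1/24) = 66.1% at 5%.

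**Set-up (Cohort 1, Scenario 2).** X1 ~ Bin(24, p) and X2 ~ Bin(44, p), independent. Part 2 opens if X1 ≥ r. Because 2/24 is discretionary, r = 2 (every 2/24 continues) and r = 3 (none does) bracket the rule.

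Mean pooled ORR given go = (E[X1 | X1 ≥ r] + 44p) / 68.

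**At p = 5%.** P(X1 = 0, 1, 2) = 0.2920, 0.3688, 0.2232. E[X1] = 24 × 0.05 = 1.2 and E[X2] = 44 × 0.05 = 2.2.

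- r = 2: P(go) = 1 − 0.2920 − 0.3688 = 0.3392. E[X1 | go] = (1.2 − 0.3688) / 0.3392 = 2.45. Pooled mean = (2.45 + 2.2) / 68 = 6.8%.
- r = 3: P(go) = 0.3392 − 0.2232 = 0.1159 (from unrounded values). E[X1 | go] = (1.2 − 0.3688 − 2 × 0.2232) / 0.1159 = 3.32. Pooled mean = (3.32 + 2.2) / 68 = 8.1%.

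The lower limit exceeds a true 5% exactly when X1 + X2 ≥ 8. Exact enumeration given go puts this at 5.13% (r = 2) and 10.85% (r = 3). No interval of a continuing trial misses on the other side, so conditional coverage is 94.87% and 89.15%.

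**Across true ORRs, given go (r = 2 / r = 3).**

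| True ORR | P(go) | Mean pooled ORR | Bias, points | Lower limit above true ORR | Coverage |
|---|---|---|---|---|---|
| 5% | 33.9% / 11.6% | 6.8% / 8.1% | 1.8 / 3.1 | 5.1% / 10.9% | 94.9% / 89.2% |
| 8% | 58.3% / 30.1% | 9.3% / 10.4% | 1.3 / 2.4 | 3.1% / 5.3% | 96.9% / 94.7% |
| 10% | 70.8% / 43.6% | 11.0% / 12.0% | 1.0 / 2.0 | 2.3% / 3.5% | 97.7% / 96.5% |
| 20% | 96.7% / 88.5% | 20.2% / 20.6% | 0.2 / 0.6 | 2.3% / 2.5% | about 97% / about 97% |

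**Over go and stop together, at 5%.**

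- P(go and ≥8/68) = 0.3392 × 0.0513 = 1.7% (r = 2), or 0.1159 × 0.1085 = 1.3% (r = 3). The plan states 2.0%.
- The intervals of stopped trials (0, 1 or 2 of 24) all contain 5%. Overall coverage is therefore 100% − 1.7% = 98.3%, or 100% − 1.3% = 98.7%.
- The reported ORR averages 3.9% (r = 2) or 4.3% (r = 3), slightly below the true value.

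**Part 2 alone (n = 44).** Its ORR is unbiased given go, and its exact interval keeps at least 95% coverage. For example, 5/44 gives 3.8% to 24.6%. The smallest count with a lower limit above 5% is 6/44 (5.2% to 27.4%), reached with probability 2.2% at 5% and 89.8% at 20%.

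**The case against.** The strongest reply is that conditioning on go is a choice. Over all outcomes the design gives a 5% drug less chance of a lower limit above 5% than Table 11.2 states, not more, and overall coverage at 5% is about 98%. That is correct. A reader might infer from 10.9% against a nominal 2.5% that the gate inflates type I error, or that the interval fails its stated coverage. The documents support neither reading: no test is planned, no conditional coverage is promised, and the 10.9% applies to only 11.6% of trials of such a drug.

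The 3.1-point bias and 89.2% coverage also rest on the strictest reading of a partly discretionary rule. If 2/24 always continues, two-sided coverage at 5% is 94.9%. Continuing after 0 or 1 responder would shrink the bias further. Under either reading coverage is above 95% by a true ORR of 10%, and at 20% the bias is negligible.

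A reader might also conclude that no selection-free estimate will ever be produced. That cannot be established, because the separate SAP was not available.

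What remains is that anyone interpreting an n = 68 result is in the go situation, and there the pooled ORR leans upward if the drug is weak. The discretion in the rule makes formal two-stage corrections awkward, but it does not affect a Part 2-only estimate.

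**Conclusion.** The point holds as one of conditional estimation, confined to low true ORRs. For Cohort 1 in Scenario 2 at a true 5%, the pooled ORR given go overstates by 1.8 to 3.1 points, and the chance of a lower limit above 5% is 5.1% to 10.9%. The bias falls to 1.0 to 2.0 points at 10% and 0.2 to 0.6 points at 20%. It is not a type I error problem, an overall-coverage failure or a reason to change the decision rule or the primary analysis.

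The figures assume exactly 24 and 44 subjects, a go decision that depends only on the responder count, and interim responders equal to final confirmed responders. The last is a simplification: the interim comes after the opportunity for two tumor assessments, and responses may be confirmed later.

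**What to change.** Keep the pooled FAS ORR with its Clopper-Pearson interval as the primary result. Before Part 2 data are seen, add to the SAP:

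1. A companion Part 2-only ORR with its Clopper-Pearson interval. In Scenario 2 this is Cohort 1 Part 2, n about 44. In Scenario 1 it is all Part 2 subjects, n about 44, with a descriptive split by HER3 cohort. The split is needed because Scenario 1 enrolls regardless of HER3 status, so the Cohort 1 share of Part 2 is not fixed. With the 50% to 75% HER3-high prevalence in Section 1.2 taken as an assumption, it would be about 22 to 33 subjects (44 × 0.50 to 44 × 0.75).
2. One sentence stating that the pooled interval does not account for the interim decision.

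The cost is one table. The downside is precision: at a true ORR of 20%, the probability of a lower limit above 5% is 89.8% at n = 44, against 97.4% at n = 68. The Part 2-only result should therefore stand beside the pooled one, not replace it.

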11.5.1.2. Secondary Efficacy Analyses

The key secondary efficacy endpoint is duration of response (DoR), defined as the time from the date of the first documentation of objective response (CR or PR) to the date of the first documentation of disease progression or death due to any cause, as assessed by BICR per RECIST v1.1. DoR will be calculated for responding subjects (PR or CR) only. Subjects who are progression-free at the time of the analyses will be censored on the date of the last adequate tumor assessment (CR, PR, or stable disease [SD]).

Other secondary efficacy endpoints include:

- ORR as assessed by Investigator per RECIST v1.1 will be analyzed in the same manner as the primary efficacy endpoint.
- DoR as assessed by Investigator per RECIST v1.1 will be analyzed in the same manner as the key secondary efficacy endpoint.
- DCR is defined as the proportion of subjects who achieved a confirmed BOR of CR, PR, or SD as assessed by BICR and Investigator per RECIST v1.1. It will be analyzed in the same manner as the primary efficacy endpoint.
- Time to response (TTR) is defined as the time between the start of study treatment to the date of the first documentation of objective response (CR or PR) that is subsequently confirmed. TTR will be assessed by BICR and Investigator per RECIST v1.1. TTR will be calculated for responding subjects (BOR of PR or CR) only.
- PFS is defined as the time from start of study treatment to the first objective documentation of radiological disease progression or death due to any cause. Subjects who are progression-free at the time of the analyses will be censored on the date of the last adequate tumor assessment (CR, PR, or SD).
- OS is defined as the time from the start of study treatment to the date of death due to any cause. Subjects who are alive at the time of the analyses will be censored on the last contact date at which the subject is known to be alive.

Distribution of time-to-event endpoints (DoR, PFS, and OS) will be estimated using the Kaplan-Meier method and results will be presented graphically. Median DoR and its 2-sided 95% CIs will be calculated using Brookmeyer and Crowley methods. In addition, the event-free probability at different time points (eg, 3, 6, 9, 12 months) will be estimated with corresponding 2-sided 95% CIs using the Greenwood formula for variance derivation. TTR will be summarized using descriptive statistics. Censoring rules for the time-to-event endpoints (DoR, PFS and OS) will be specified in the SAP.

No formal comparison between the two cohorts is planned.

Descriptive statistics for the best percent change from baseline in the SoD will be provided by cohort, if applicable. A waterfall plot of the best percent change in the SoD and a swimmer's plot for response over time will also be prepared.

The correlation between HER3 protein expression level (as determined by HER3 IHC assay) and efficacy will be assessed.

11.5.1.3. Exploratory Efficacy Analyses

Analyses to explore the relationship between exposure and efficacy may be conducted using data from this study, or may be conducted using pooled data with other studies. If conducted, such analyses will be reported separately and will therefore not be part of the CSR.

11.5.1.4. Multiplicity Adjustment

Not applicable.

11.5.2. Safety Analyses

Safety analyses will be performed using the Safety Analysis Set and in general will be descriptive. Additional details regarding safety analyses will be described in the SAP.

The overall study period will be divided into three mutually exclusive segments:

- Pre-treatment period: from date of study informed consent (inclusive) to the start date of study treatment – 1;
- On-treatment period: from the start date of study treatment (inclusive) to 47 days after the end date of study treatment (inclusive);
- Post-treatment period: starting from 48 days after the end date of study treatment.

Safety summaries will include assessments collected during the on-treatment period unless otherwise specified. Data will be summarized by cohort if applicable. All assessments will be listed.

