| To evaluate the safety and tolerability of U3-1402 in subjects with advanced or metastatic CRC | 
Title: TEAEs and other safety parameters during the study*
 
Description: Descriptive statistics of safety endpoints
 
Time frame: From the time the subject signs the main study ICF and up to 40 (+ 7) days after the last dose of study drug (ie, 5 half-lives of the ADC/the follow-up period)
 
*Although this is a secondary objective, this is a primary outcome measure.
 | Incidence of TEAEs, SAEs, AESIs (ILD and elevation of aminotransferases and TBL), ECOG PS, vital sign measurements, standard clinical laboratory parameters. AEs will be coded using the most recent version of MedDRA and will be graded using NCI-CTCAE v5.0. | Safety |
| To evaluate HER3 protein expression in tumor tissue and its relationship with efficacy | 
Title: Correlation between HER3 protein expression (as determined by HER3 IHC assay) and efficacy
 
Description: Based on a descriptive summary of the efficacy endpoints and HER3 status, a correlative analysis between HER3 protein expression level (as determined by HER3 IHC assay) and efficacy may be performed.
 
Time frame: Efficacy data are collected at baseline, then from the start of study treatment until disease progression or death, lost to follow-up, or withdrawal of consent by the subject.
 
HER3 data are collected at baseline (archival and pre-treatment tumor biopsy) and at Cycle 2.
 | HER3 protein expression in tumor tissue (as determined by IHC) and correlation with efficacy | Efficacy/ Biomarker |

| Objectives | Outcome Measures | Endpoints | Category |
|---|--|--|---------------------|
| To assess the immunogenicity incidence against U3-1402 | 
Title: Immunogenicity
 
Description: ADA prevalence, incidence, and titer for U3-1402
 
Time frame: Data are collected from the start of study treatment until the end of treatment. Additional timepoints are specified in Table 13.1.
 | 
ADA prevalence: The proportion of all subjects having a confirmed positive ADA sample at any point in time.
 
ADA incidence: The proportion of subjects having treatment-emergent ADA.
 
ADA titer will be determined for confirmed ADA-positive samples.
 
Neutralizing antibodies: When neutralizing assay becomes available confirmed ADA-positive samples may be analyzed for neutralizing activity.
 | Immuno- genicity |

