9.2. Adverse Event Collection and Reporting

All clinical AEs occurring after the subject signs the main study ICF and up to 47 days after the last dose of study drug (ie, the follow-up period), whether observed by the Investigator or reported by the subject, will be recorded on the AE eCRF. When an AE of potential ILD (Section 9.3.1) is observed after 47 days since last dose of U3-1402, the AE (serious or non-serious) should be reported and recorded in AE eCRF if it is considered related to U3-1402. Medical conditions (including clinical laboratory values/vital signs that are out of range) that were diagnosed or known to exist prior to informed consent will be recorded as part of medical history.

All AEs, AESIs, events of overdose, and SAEs are to be reported according to the procedures in Section 9.5.

All clinical laboratory results, vital signs, and ECG results or findings should be appraised and documented by the Investigator to determine their clinical significance. Isolated abnormal clinical laboratory results, vital sign findings, or ECG findings (ie, not part of a reported diagnosis) should be reported as AEs if they are symptomatic, lead to study drug discontinuation, dose reduction, require corrective treatment, or constitute an AE in the Investigator's clinical judgment.

At each time point, the Investigator will determine whether any AEs have occurred by evaluating the subject. Adverse events may be directly observed, reported spontaneously by the subject or by questioning the subject (or, when appropriate, by a caregiver, surrogate, or the subject's legally authorized representative) at each time point. Subjects should be questioned in a general way, without asking about the occurrence of any specific symptoms. The Investigator must assess all AEs to determine seriousness, severity, and causality, in accordance with the definitions in Section 9.4. The Investigator and any qualified designees are responsible for detecting, documenting, and recording events that meet the definition of an AE or SAE and remain responsible for following AEs that are serious, considered related to the study drug or study procedures, or that caused the subject to discontinue U3-1402. The Investigator's assessment must be clearly documented in the study site's source documentation with the Investigator's signature.

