11.5.2.1. Adverse Event Analyses

TEAEs are defined as those AEs with a start or worsening date during the on-treatment period.

AEs will be coded using MedDRA and graded based on v5.0 of NCI-CTCAE.

The number and percentage of subjects with TEAEs will be summarized by system organ class (SOC), and/or PT. Additional summaries will be provided by the worst CTCAE grade, relationship to the study treatment (ie, regardless of relationship to study drug, study drug related), seriousness, actions taken with study treatment (ie, associated with dose reduction, dose interruption, study treatment discontinuation), and fatality.

AESIs will also be summarized.

All deaths and on-treatment deaths will be summarized by primary cause of death. All deaths will be listed.

A by-subject AE (including TEAE) data listing will be provided including, but not limited to, verbatim term, PT, SOC, NCI-CTCAE grade, and relationship to study drug. SAEs, AESIs and TEAEs associated with treatment discontinuation will be listed.

SAEs starting or worsening after the on-treatment period, if reported as related to study treatment, will be listed separately.

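### Drug-related ILD that starts after the on-treatment period is collected and listed but enters no planned table, and non-serious cases also miss the separate late-event listing

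*Combined protocol and SAP*

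**What the plan says.** **Collection.** Section 9.2 records AEs up to 47 days after the last dose and then makes an exception for one event type. A potential ILD event that "is observed after 47 days since last dose of U3-1402, the AE (serious or non-serious) should be reported and recorded in AE eCRF", on the condition that "should be reported and recorded in AE eCRF if it is considered related to U3-1402".

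**Analysis window.** Section 11.5.2 defines the on-treatment period as running "from the start date of study treatment (inclusive) to 47 days after the end date of study treatment (inclusive"), and sets the default: "Safety summaries will include assessments collected during the on-treatment period unless otherwise specified".

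**AESI output.** Section 11.5.2.1 says only "AESIs will also be summarized". It names no window of its own.

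**Late events.** Section 11.5.2.1 provides one output specifically for events after that period: "SAEs starting or worsening after the on-treatment period, if reported as related to study treatment, will be listed separately".

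**Endpoint time frame.** Table 2.1 (and the synopsis) list AESI incidence, naming ILD, and collect it from main consent "up to 40 (+ 7) days after the last dose of study drug". The table calls this a primary outcome measure although the objective is secondary.

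**Other routes.** Section 11.5.2 also promises that every assessment will be listed. Section 11.5.2.1 promises a by-subject AE listing that is not confined to TEAEs, and an AESI listing. Section 13.2.5 asks the ILD Adjudication Committee to assess ILD prevalence at the end of the study. None of these states a 47-day limit.

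**The concern.** The collection rule and the summary rule do not match. ILD is the one important identified risk named in Section 1.2.2, and Section 9.3.1 has every ILD event followed to resolution, including after the drug is stopped. Section 9.2 extends the recording of related ILD beyond day 47, yet no planned table uses those records.

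The mismatch is sharpest for non-serious cases. Sections 9.2 and 9.5 already require any late serious event judged related to be reported as an SAE, and the late listing takes those. What the ILD exception adds to that general rule is the non-serious related cases, and these are the ones the separate late listing leaves out.

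At stake is the ILD percentage a reader of the study report will quote. If a late case occurs in a subject with no on-treatment ILD, that percentage will be lower than the number of subjects with recorded related ILD would suggest, and nothing in the table will say so.

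**Working it through.** The plan states no ILD rate, so there is no figure of its own to reproduce on this point. The check has two parts.

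**1. Where a late related case would go under the text as written**

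| Planned output | Serious, related, late | Non-serious, related, late |
|---|---|---|
| AE eCRF (9.2) | yes | yes |
| By-subject AE listing and AESI listing (11.5.2.1) | yes | yes |
| Separate late-event listing (11.5.2.1) | yes | no |
| AESI summary table (11.5.2 default, 11.5.2.1) | no | no |

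The last row rests on the default in Section 11.5.2, which yields only where something else is specified. For AESIs nothing else is. For deaths it is: Section 11.5.2.1 summarises all deaths as well as on-treatment deaths. So the authors name a wider scope where they want one.

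**2. What one omitted case is worth**

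Inputs: about 80 treated subjects if either Part 2 scenario goes ahead, and about 36 if both cohorts stop (Section 11.3). Case counts are assumptions, because the documents give none.

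Reduction in the tabulated rate = (subjects whose only ILD is late and related) / N. It cannot be negative.

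- N = 80: 1/80 = 1.25 points per subject
- N = 36: 1/36 = 2.78 points per subject

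Illustrations with Clopper-Pearson 95% intervals:

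| N | Assumed on-treatment cases | Tabulated | With one late case counted |
|---|---|---|---|
| 80 | 0 | 0% (0 to 4.5%) | 1.25% (0.03 to 6.8%) |
| 80 | 2 | 2.5% (0.3 to 8.7%) | 3.75% (0.8 to 10.6%) |
| 36 | 2 | 5.6% (0.7 to 18.7%) | 8.3% (1.8 to 22.5%) |

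The chance of at least one such case is 1 − (1 − p)^N, where p is the per-subject risk of late-only related ILD. Over an assumed range:

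| p | N = 80 | N = 36 |
|---|---|---|
| 0.5% | 33% | 16.5% |
| 1% | 55% | 30% |
| 2% | 80% | 52% |
| 3% | 91% | 67% |

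**3. The two windows may not start on the same day**

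Section 9.2 counts from the last dose. Section 11.5.2 counts from the end date of study treatment, which it does not define. Section 6.4 defines end of treatment as the date the investigator decides to stop. Section 5.4.1.1 allows a delay of up to 49 days from the last infusion. If the decision to stop falls on day 49 and that date is used, the on-treatment period reaches 49 + 47 = 96 days after the last dose. Some events treated as late by Section 9.2 would then count as on-treatment. This narrows the gap for some subjects and leaves it in place for others.

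**The case against.** The strongest reply is that nothing is lost. The by-subject AE listing and the AESI listing carry no window, so a late non-serious case would be visible in both. The adjudication committee's end-of-study prevalence is a second route to an ILD figure, also without a stated window. Serious late cases have their own listing, and fatal ones enter the all-deaths summary. Section 11.5.2 leaves further safety detail to a SAP that is still to be finalised. The window is also prespecified and reasoned, since Table 2.1 ties it to five half-lives of the ADC. After day 47, ascertainment changes: ILD need be recorded only if judged related, and survival contact may be by telephone. One pooled rate would mix all-causality with related-only events.

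Most of this stands, and it limits the point. A reader might infer that late ILD cases disappear, or that overall ILD incidence will certainly be understated. The documents do not support either. The cases are listed, and any shortfall is confined to the AESI table and arises only if such a case occurs. The on-treatment figure is also not wrong for the window it describes.

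What the reply does not remove is the missing table. A listing is not an incidence. Section 13.2.5 sends the committee's findings to the sponsor, and Section 11 plans no analysis of adjudicated ILD. A SAP still to be written can close the gap, but until it does the default excludes late ILD.

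**Conclusion.** The point holds in a limited form. Followed as written, the plan collects and lists drug-related ILD arising after the on-treatment period but leaves it out of the tabulated ILD incidence, and non-serious cases also miss the separate late-event listing. If such a case occurs in a subject without on-treatment ILD, the tabulated rate is lower by 1.25 points at N = 80 or 2.78 points at N = 36 than if it were counted. With no such case the effect is zero.

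This assumes that the later SAP adds no exception, that the Section 11.5.2 default governs the AESI summary, and that the end date of study treatment lies close to the last dose. The late-onset rate is not in the documents, so the size of any shortfall cannot be stated.

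**What to change.** In Section 11.5.2.1, or in the SAP before it is finalised:

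- Keep the on-treatment ILD AESI summary as it is.
- Add a separate row for drug-related ILD with onset at any time after first dose, by investigator judgement and, where available, as adjudicated drug-related. Label it as related-only after the on-treatment period. It should not be pooled with the on-treatment summary, and it cannot be widened to all potential ILD, because non-serious unrelated cases after day 47 need not be recorded.
- Extend the separate late-event listing to related ILD of any seriousness.
- State whether the end date of study treatment means the last-dose date, so that the collection and analysis windows match.

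The cost is a sentence or two of text, one table row and a wider listing criterion. Section 9.2 already collects the related cases, so no new data are needed. The drawback is that the added row rests on related-only ascertainment after day 47, which the label must make plain.
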